1.0 OBJECTIVES

1.1 Primary Objective

- a. To test whether the complete remission (CR) rate (including CR with incomplete recovery [CRi]) in poor-risk patients with acute myeloid leukemia (AML) treated with a combination of chemotherapy and pravastatin is sufficiently high to warrant Phase III investigation. This will be tested independently in two groups of patients: (1) patients with MDS transformed to AML, and (2) refractory or relapsed patients with previous remission < 6 months.

1.2 Secondary Objectives

- a. To estimate the frequency and severity of toxicities of this regimen in these two groups of patients.

1.3 Other Objectives

- a. To estimate relapse-free survival and overall survival rates in these two groups of patients.
- b. To evaluate in a preliminary manner whether prestudy cytogenetic features correlate with response in these two groups of patients.

2.0 BACKGROUND

Acute myelogenous leukemia (AML) is a difficult disease to treat. Although 65% of patients achieve CR with chemotherapy, only 15-30% of these patients remain free of disease for five years because of the high incidence of relapse. (1) Another 10-20% of patients have refractory AML and never achieve CR with induction chemotherapy. (1) Over the last several years, there has been excitement about the possibility of combining biologically targeted therapy in the treatment of various diseases including AML. Although AML is genetically heterogeneous, AML cells do share biologic characteristics that make molecular targeted therapies potentially effective. This study will evaluate chemotherapy in combination with pravastatin.

Cholesterol and AML

Cholesterol homeostasis is abnormal in AML cells, with cholesterol synthesis and LDL processing being hyperactive in cultured AML cells. (2-5) Cultured AML cells frequently overexpress the genes for low-density lipoprotein receptor (LDL), 3-hydroxy-3-methylglutaryl coenzyme A reductase (HMG-CoAR), synthesize cholesterol at a higher level, and import more cholesterol. (6) Patients with AML often have hypercholesterolemia at the time of diagnosis, but this typically resolves when patients achieve a complete remission. (2,7) This suggests that AML cells require high levels of cholesterol for their survival, and that abnormalities in cholesterol homeostasis protect AML cells. (2) Therefore, the cholesterol pathway may be a valid target in the treatment of AML. In vitro, simvastatin, an HMG-CoA reductase inhibitor, inhibits AML cell growth. (8) HMG CoA reductase is the major regulatory enzyme of the mevalonate pathway. Mevalonate constitutes the precursor of isoprene units incorporated into sterol and non-sterol compounds such as cholesterol. Blocking protein geranylgeranylation appears to be essential for statin-induced apoptosis of human AML cells. (9)

Rationale for combining pravastatin with chemotherapy:

Cholesterol levels further increase in many AML cells treated with chemotherapy. (6,10) This occurs by chemotherapy increasing the level of LDL receptor and HMG-CoA reductase mRNA levels in AML cells. (2) Conversely, inhibiting cholesterol synthesis sensitizes AML cells to cytotoxic therapy. (6,11,12) This was the basis of a recently published Phase I study combining pravastatin with idarubicin and intermediate dose cytarabine. (6) This study demonstrated the safety of combining pravastatin with intermediate dose cytarabine and idarubicin. (6) Pravastatin

was chosen because of its high bioavailability, and because it is not substantially metabolized by the cytochrome p450 system. (6) Many other treatments and supportive care medications used in the treatment of AML patients (i.e. antifungals) are CYP substrates; therefore, choosing a statin that is not metabolized by the CYP system is important. A maximum tolerated dose (MTD) for pravastatin and idarubicin/intermediate dose cytarabine was not reached. However, pharmacokinetic studies demonstrated higher and more sustained serum pravastatin levels with pravastatin doses above 1,280 mg/day. (6) The CR and CRp rates were encouraging (including 8 of 10 with unfavorable cytogenetics and 9 of 22 salvage patients), suggesting that Phase II evaluation of this approach is warranted.

S0919 was initially designed for patients with relapsed AML, where the patient's preceding remission had lasted ≥ 3 months. The null response rate was 30%. The study closed to accrual on Nov 1, 2012 after meeting the defined criterion for a positive study; and the results are being submitted to the American Society of Clinical Oncology meeting. Based on the promising results from this trial, the trial has now been amended to evaluate this therapeutic regimen in poor-risk patients (patients with newly diagnosed AML arising out of myelodysplastic syndrome, primary refractory AML, and relapsed AML with the patient's preceding remission lasting < 6 months).

Inclusion of Women and Minorities

This study was designed to include women and minorities, but was not designed to measure differences of intervention effects.

Since HIV-positive patients are immunocompromised and most are treated with already myelosuppressive antiretroviral regimens, they may not tolerate intensive chemotherapies. Therefore, patients with HIV infection will be excluded from this study, if they do not meet the parameters that are felt will allow safe participation in this study. HIV infected patients with no history of AIDS defining events, sufficient CD4 cell count, acceptable viral load and who are not receiving the myelosuppressive agents zidovudine or stavudine will be included in this study (see [Section 5.1I](#)).

3.0 DRUG INFORMATION

Investigator's Brochures

For information regarding Investigator's Brochures, please refer to SWOG Policy 15.

For this study, AraC, idarubicin and pravastatin are commercially available; therefore, Investigator Brochures are not applicable to these drugs. Information about commercial drugs is publicly available in the prescribing information and other resources.

3.1 Cytosine Arabinoside (Ara-C) (Cytarabine) (Cytosar U) (NSC-63878)

a. DESCRIPTION

AraC is chemically 4-amino-1-S-D-arabino-furanosyl-2(1H)-primidinone. AraC is metabolized to its active form, ara-CTP. The ara-CTP functions as an inhibitor of DNA polymerase. Ara-C exhibits cell phase specificity, killing cells undergoing DNA synthesis (S phase) and may also block cells from progressing to S phase from G1. Extensive chromosomal damage, including chromatid breaks, occurs. AraC appears to be most effective in tumors with high growth fraction.

b. TOXICOLOGY

Human Toxicology: Side effects of AraC include myelosuppression, nausea, vomiting, diarrhea, anorexia, anal ulceration, stomatitis, rash, headache, fever, myalgia, malaise, bone pain, chest pain, hepatic and renal dysfunction, and alopecia. Central nervous system toxicity, i.e., significant cerebral and cerebellar dysfunction, progression to coma, has been seen with high doses. Severe cardiomyopathy has been reported with high dose AraC in combination with cyclophosphamide. Progressive ascending paralysis has occurred in two patients receiving IV and intrathecal AraC. Marked keratoconjunctivitis has also occurred with high doses.

The most frequently reported reactions after intrathecal administration were nausea, vomiting and fever. Paraplegia and meningitis have been reported with intrathecal administration. AraC given intrathecally may cause systemic toxicity and careful monitoring of the hemopoietic system is indicated. If used intrathecally or if high dose therapy is used, do not use a diluent containing benzyl alcohol.

AraC can cause fetal harm when administered to a pregnant woman, however, there are no adequate and well controlled studies in pregnant women.

c. PHARMACOLOGY

Kinetics: AraC is metabolized by deoxycytidine kinase and related kinases to nucleotide triphosphate, which is an active inhibitor of DNA polymerase. Deoxycytidine prevents or delays cytotoxic activity. The active form is converted to nontoxic uracil derivatives by pyrimidine nucleoside deaminases. The balance of kinase and deaminase levels appears to be an important factor in sensitivity/resistance of the cell to AraC. After IV injection, plasma disappearance of ara-C is biphasic. Initial half-life is 10 minutes, delayed half-life is 1 - 3 hours. After 24 hours, 80% is excreted in the urine as its inactive metabolite, Aral. After a single IV administration of AraC, levels in CSF are low. With intrathecal administration, half-life is 2 hours. There is little conversion to AraU because of low CSF levels of deaminase. Drug interaction of AraC has been reported with digoxin, gentamycin and fluorocytocine.

Formulation: AraC is supplied as a sterile powder in 100 mg and 500 mg vials for injection. AraC is also available in 1 and 2 gram vials. The drug should be reconstituted with sterile water for injection.

Storage and Stability: The sterile powder should be stored at room temperature 15° - 30°C (59° - 86°). The resulting solution has a stability of 48 hours if stored at ROOM TEMPERATURE. Do not use if even a slight haze develops. The reconstituted solution may be further diluted in 5% Dextrose or sodium chloride injection.

Administration: AraC is usually administered by continuous IV infusion, but IV bolus and subcutaneous use have their place in treating certain leukemic responses (i.e., maintenance or remission). In this study, AraC will be administered by continuous infusion.

Supplier: AraC is commercially available and therefore should be purchased by a third party. This drug will NOT be supplied by the NCI.

Please refer to the package insert for complete information.

3.2 Idarubicin HCL (Idamycin®) (NSC-256439)

a. DESCRIPTION

A sterile, synthetic antineoplastic anthracycline for intravenous use. Idarubicin is a DNA-intercalating analog of daunorubicin which has an inhibitory effect on nucleic acid synthesis and interacts with the enzyme topoisomerase II.

b. TOXICOLOGY

Idarubicin is a potent bone marrow suppressant. Idarubicin should not be given to patients with pre-existing bone marrow suppression induced by previous drug therapy. Deaths due to infection and/or bleeding have been reported during the period of severe myelosuppression. Other warnings include pre-existing heart disease, previous therapy with anthracyclines, previous radiation to the mediastinal-pericardial area, myocardial toxicity typically presenting as CHF, and arrhythmias or other cardiomyopathies. Other risks include bone marrow depression, infections, leukemic pericarditis and/or myocarditis, and renal or hepatic impairment. The most common side effects (90% to 100%): infection. Other common side effects include (20% to 90%): nausea, vomiting, hair loss, abdominal cramps, diarrhea, hemorrhage, mucositis, dermatologic, mental status, pulmonary-clinical, fever, headache. Other less common side effects include (10% to 20%): cardiac-clinical. Infrequent side effects include (1% to 10%): Neurologic-peripheral nerves, pulmonary allergy, seizure, cerebellar. Rare side effects include (less than 1%): None reported in this range.

c. PREGNANCY AND LACTATION

Pregnancy Category D- Idarubicin was embryotoxic and teratogenic in the rat. Idarubicin was embryotoxic but not teratogenic in the rabbit. There is no conclusive information about idarubicin adversely affecting human fertility or causing teratogenesis. It is not known whether this drug is excreted in human milk. Because many drugs are excreted in human milk and because of the potential for serious adverse reactions in nursing infants from idarubicin mothers should discontinue nursing prior to taking this drug. There has been one case reported of fetal fatality after maternal exposure to idarubicin during the 2nd trimester.

d. PHARMACOLOGY

Kinetics: The plasma concentrations follow a 2 or 3 compartment mode. Idarubicin has a rapid distribution phase with a high volume of distribution reflecting extensive tissue binding. Idarubicin undergoes extensive extrahepatic metabolism and a rapid distribution phase. Idarubicin has a very high volume of distribution. Elimination occurs predominantly by biliary and to a lesser extent by renal excretion. The mean terminal half-life is 22 hours when used as a single agent and 20 hours when used in combination. Elimination exceeds 45 hours.

Formulation: Idarubicin is a sterile, red-orange, isotonic parenteral preservative-free solution. It is available in 5mg/5ml, 10mg/10ml and 20mg/20ml single use only vials.

Storage and Stability: Idarubicin should be stored under refrigeration 2° - 8°C (36° to 46 °F), and protected from light. The vials are preservative-free and are for single use only.

Administration: Idarubicin should be administered over 10 - 15 minutes into a freely flowing line of NS or D5W. Unless there is specific data do not mix idarubicin with other drugs. Prolonged contact in an alkaline pH will degrade idarubicin. Precipitation occurs with heparin. Extravasation can cause severe local tissue necrosis. Extravasation may occur with or without an accompanying burning sensation and even if blood returns well on aspiration of the infusion needle. If extravasation occurs terminate infusion immediately and restart in another vein. Treat extravasation with intermittent ice packs (Place ice pack on area of extravasation for 1/2 hour immediately, then for 1/2 hour four times a day for 3 days) and elevate the affected extremity. For more information see package insert and seek further medical treatment as deemed necessary.

Supplier: Idarubicin HCL is commercially available and therefore should be purchased by a third party. This drug will NOT be supplied by the NCI.

Please refer to the package insert for complete information.

3.3 Pravastatin Sodium (NSC-740787)

a. DESCRIPTION

Pravastatin sodium is a 3-hydroxy-3-methylglutaryl-coenzyme (HMG-CoA) reductase inhibitor. HMG-CoA reductase catalyzes the early rate-limiting step of cholesterol biosynthesis, the conversion of HMG-CoA to mevalonate. The competitive inhibition of this enzyme results in reduced cholesterol biosynthesis.

b. TOXICOLOGY

Human toxicology: Side effects of pravastatin include chest pain, headache, fatigue, dizziness, rash, nausea, vomiting, diarrhea, heartburn, transaminase increase, myalgia, cough, and reversible cognitive side effects.

There have been case reports of hyperglycemia, increased levels of glycosylated hemoglobin (HbA1c), anaphylaxis, jaundice, cirrhosis, hepatitis, rhabdomyolysis, and Stevens-Johnson syndrome.

Safety in pregnant women has not been established. It is recommended that pravastatin be discontinued as soon as pregnancy is recognized.

c. PHARMACOLOGY

Kinetics: Pravastatin reduces the available intracellular amount of cholesterol after taken orally. This results in an increase in LDL-receptors and enhanced clearance of LDL from the serum. Pravastatin also inhibits LDL production by blocking the synthesis of VLDL, which is a building block for LDL. Pravastatin is rapidly absorbed producing peak levels 1 to 1.5 hours after taking the oral tablet. The half-life of the parent compound is 2-3 hours with 20% of the dose being excreted in the urine and 70% in the feces.

Formulation: Pravastatin is available as an oral tablet in 10 mg, 20 mg, 40 mg, and 80 mg tablets.

Storage and Stability: Pravastatin tablets should be stored at room temperature for distribution by Fisher-Acculogix (25°C) with excursions allowed to 15-30°C (59-86 °F). Tablets should be protected from moisture and light.

Administration: For this study, pravastatin should be administered as a single dose (over up to 2 hours) once daily in the morning. It can be taken with or without food.

Supplier and Drug Ordering: For this study, pravastatin will be supplied free of charge by Bristol-Myers Squibb.

Initial Orders: Institutions may order pravastatin after local IRB approval of the protocol. The IRB approval date will be required at the time of drug order. Orders should be placed at the time of IRB approval. Do not wait until the time of patient registration as drug may not arrive in time to begin treatment. Participating institutions are instructed to order from Bristol-Myers Squibb via e-mail to [contact] by submitting the Bristol-Myers Squibb order form (which is located on the protocol abstract page at www.swog.org). Please note: Both the SWOG study ID (**S0919**) and the BMS ID (CV123-285) will be required and must be recorded in the subject line of the e-mail request. Drug will be shipped within five days from receipt of Drug Order Form. Drug is shipped overnight Monday-Thursday for delivery on Tuesday-Friday. Drug will not be shipped on weekends or holidays. Only study drug ordered for this study may be used for protocol treatment.

Re-Supply: Send re-supply requests to [contact]. Check "re-supply" on the drug supply form. The number of patients currently on study at the requesting institution will be required at the time of drug re-order. Re-supply requests should be submitted at least 5-7 business days prior to the expected delivery date. Deliveries will be made Tuesday-Friday. When assessing need for re-supply, institutions should keep in mind the number of pills used for treatment and that shipment may take 5 days from BMS receipt of request.

Drug Returns: Unused drug supplies should NOT be returned. Unused drug should be destroyed per local institutional guidelines.

Drug Accountability: The investigator, or a responsible party designated by the investigator, must maintain a careful record of the receipt, disposition, and disposal of all drugs received from the supplier using the NCI Oral Drug Accountability Record Form (NCI Oral DARF) available at <http://ctep.cancer.gov>.

Question about drug orders, returns, or accountability should be addressed to the Fisher-Accugix IS Coordinator. Contact information is provided on the drug order form.

Please refer to the product's package insert for full prescribing and toxicity information.

4.0 DIAGNOSTIC AND STAGING CRITERIA

4.1 Diagnostic Criteria ([13-15](#))

a. Definitions:

1. Bone marrow cellularity: The volume of hematopoietic nucleated cells, expressed as a percentage of marrow volume less volume of fibrosis.
2. Blasts: For AML, the following cell types are considered equivalent to blasts and are included in the calculation of blast percentages. Note that erythroblasts are **not** counted as blasts in calculating blast percentages.

CLOSED EFFECTIVE 09/01/2017

- i. Myeloblasts include both agranular and granular variants.
 - ii. Neoplastic promyelocytes, for Acute Promyelocytic Leukemia. Neoplastic promyelocytes are defined as promyelocytes with heavy granulation and irregular nuclei and/or primitive promyelocytes with very large numerous Auer rods.
 - iii. Monoblasts and promonocytes for Acute Monoblastic and Monocytic Leukemia.
 - iv. Megakaryoblasts for Acute Megakaryoblastic Leukemia.
3. Bone Marrow Blast Percentage is calculated as the percent of blasts among all nucleated marrow cells.
- b. Acute Myeloid Leukemia (AML) is a clonal expansion of myeloid blasts in bone marrow, blood or other tissue, ICD-O code 9861/3.
- The most significant change from the FAB classification is that the requisite blast percentage for a diagnosis of acute myeloid leukemia be $\geq 20\%$ myeloblasts in the blood or marrow.
- There are two exceptions to this rule. Acute erythroleukemia (erythroid/myeloid subtype) is defined by the presence in the bone marrow of greater than or equal to 50% erythroid precursors in the entire nucleated cell population and greater than or equal to 20% myeloblasts in the non-erythroid cell population. Pure erythroid leukemia is defined as a neoplastic proliferation of immature cells committed exclusively to the erythroid lineage ($> 80\%$ of the marrow nucleated cells) with no evidence of a significant myeloblastic component.
- c. Myelodysplastic Syndrome (MDS) is defined according to WHO criteria. (15)
- d. WHO Classification of AML, with the following additions and clarifications. (15)

WHO histological classification of acute myeloid leukemias

	ICD-O Code	FAB Equivalent
Acute myeloid leukemia with recurrent genetic abnormalities		
Acute myeloid leukemia with t(8;21)(q22;q22); (AML 1/CBF α)/ETO)	9896/3	
Acute myeloid leukemia with abnormal bone marrow eosinophils inv(16)(p13q22) or t(16;16)(p13;q22); (CBF β /MYH11)	9871/3	
Acute promyelocytic leukemia (AML with t(15;17)(q22;q12) (PML/RAR α) and variants	9866/3	M3
Acute myeloid leukemia with 11q23 (MLL) abnormalities	9897/3	
Acute myeloid leukemia with multilineage dysplasia	9895/3	
Acute myeloid leukemia and myelodysplastic syndromes, therapy-related	9920/3	

Acute myeloid leukemia not otherwise categorized	9861/3	
Acute myeloid leukemia minimally differentiated	9872/3	M0
Acute myeloid leukemia without maturation	9873/3	M1
Acute myeloid leukemia with maturation	9874/3	M2
Acute myelomonocytic leukemia	9867/3	M4
Acute monoblastic and monocytic leukemia	9891/3	M5a, M5b
Acute erythroid leukemias	9840/3	M6a, M6b
Acute megakaryoblastic leukemia	9910/3	M7
Acute basophilic leukemia	9870/3	
Acute panmyelosis with myelofibrosis	9931/3	
Myeloid sarcoma	9930/3	
Acute leukemia of ambiguous lineage	9805/3	
Undifferentiated acute leukemia	9801/3	
Bilineal acute leukemia	9805/3	
Biphenotypic acute leukemia	9805/3	

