5.1 Induction Registration (Step 1)

- _____ a. For patients registered to the relapsed/refractory cohort (Cohort 2), patients must have a previous morphologically confirmed diagnosis of acute myeloid leukemia (AML).

For patients registered to the MDS transformed to AML cohort (Cohort 1), patients must have a previous morphologically confirmed diagnosis of MDS/CMML. Patients may have received previous non-intensive therapy (e.g. azacitadine, decitabine, low-dose cytarabine (LDAC), lenalidomide) given for treatment of MDS/CMML (with up to 20% blasts). At the time of registration they must have a morphologically confirmed diagnosis of AML.

Note: This protocol uses the WHO diagnostic criteria for AML (see [Section 4.1](#)). Patients with acute promyelocytic leukemia (APL, FAB, M3) or blastic transformation of chronic myelogenous leukemia are not eligible.

- _____ b. Patients must NOT have received autologous or allogeneic stem cell transplantation.

Patients in the relapsed/refractory AML cohort (Cohort 2), must meet all of the following additional criteria:

1. Patient must have received at least one prior Induction chemotherapy regimen for their AML;
 - they may have received any type of chemotherapy
 - administration of hydroxyurea to control high WBC prior to, during, and after registration is permitted
2. Relapse or refractory disease must be documented by a bone marrow examination demonstrating > 5% blasts in the bone marrow not attributable to another cause;
3. Patient must NOT have received chemotherapy within 14 days prior to registration;

- _____ d. Primary refractory patients will be eligible if, on Day 14 of their previous chemotherapy regimen, they have significant residual disease. Patients who received only hypomethylating agent or low dose therapy for Induction are not considered primary refractory for purposes of this study and are not eligible.

- _____ e. Relapsed patients must have achieved a complete remission (CR) or CR with incomplete blood count recovery (CRi) lasting < 6 months with their last induction regimen.

SWOG Patient No. _____

Patient's Initials (L, F, M) _____

5.1 Induction Registration (Step 1) (contd.):

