10.0 CRITERIA FOR EVALUATION AND ENDPOINT DEFINITIONS

10.1 Remission Definitions: (13)

- a. Morphologic complete remission (CR): ANC \geq 1,000/mcl, platelet count \geq 100,000/mcl, $<$ 5% bone marrow blasts, no Auer rods, no evidence of extramedullary disease. (No requirements for marrow cellularity, hemoglobin concentration).
- b. Morphologic complete remission with incomplete blood count recovery (CRi): Same as CR but ANC may be $<$ 1,000/mcl and/or platelet count $<$ 100,000/mcl.
- c. Partial remission (PR): ANC \geq 1,000/mcl, platelet count $>$ 100,000/mcl, and at least a 50% decrease in the percentage of marrow aspirate blasts to 5-25%, or marrow blasts $<$ 5% with persistent Auer rods.

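### In Cohort 1, a marrow that still meets the protocol's own definition of acute erythroid leukemia can satisfy the CRi criterion

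*Combined protocol and SAP*

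**What the plan says.** **Blast percentage (protocol 4.1a).** Item 2 says that "erythroblasts are not counted as blasts in calculating blast percentages". Item 3 says "Bone Marrow Blast Percentage is calculated as the percent of blasts among all nucleated marrow cells". The document contains no other definition of a marrow blast percentage.

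**Diagnosis (4.1b, 4.1d).** AML normally needs at least 20% myeloblasts, with two exceptions. The erythroid/myeloid subtype needs "greater than or equal to 50% erythroid precursors in the entire nucleated cell population" together with "greater than or equal to 20% myeloblasts in the non-erythroid cell population". For the other, "Pure erythroid leukemia is defined as a neoplastic proliferation of immature cells committed exclusively to the erythroid lineage", at more than 80% of nucleated marrow cells and "with no evidence of a significant myeloblastic component". The classification in 4.1d lists the acute erythroid leukemias (M6a, M6b) as AML.

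**Eligibility (5.1a, 5.1b).** Section 5.1a applies the 4.1 criteria and excludes only acute promyelocytic leukemia and blastic transformation of CML. Cohort 1 patients have prior MDS or CMML, and "At the time of registration they must have a morphologically confirmed diagnosis of AML". No minimum blast percentage on the 4.1a scale is set for them. For Cohort 2, item 2 of 5.1b requires more than 5% marrow blasts.

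**Response (10.1).** CR requires recovered neutrophils and platelets and fewer than "5% bone marrow blasts, no Auer rods, no evidence of extramedullary disease". CRi is the same with the count thresholds waived. Neither requires a change from baseline or mentions erythroid cells.

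**Decision rule (11.2).** In each cohort of 37, 12 or more CR or CRi count as success. The stated critical level is 0.05 at a true rate of 20% and the stated power is 0.87 at 40%.

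**The concern.** Section 4.1b recognises that the ordinary blast percentage does not describe erythroid disease, and it corrects for this at diagnosis. Section 10 does not carry the correction over to response. In the affected patients the quantity that must fall below 5% can already be below 5% at registration, so the criterion cannot tell a cleared marrow from an unchanged one.

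At stake is the primary endpoint. CR plus CRi is compared with a sharp count threshold, so one or two misclassified patients can decide a cohort. The same measure feeds the marrow part of the relapse definition in 10.3.

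**Working it through.** **1. The plan's own figures.** With n = 37 and success at 12 or more, the exact binomial gives
- P(X ≥ 12 | p = 0.20) = 0.0517, which is 0.05 at the precision printed in 11.2;
- P(X ≥ 12 | p = 0.40) = 0.8667, which is 0.87 as printed.

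The rule is sound if responses are classified correctly.

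**2. Baseline blast percentage, erythroid/myeloid subtype.** Let E be the erythroid share of all nucleated cells (at least 50%) and b the myeloblast share of non-erythroid cells (at least 20%), both from 4.1b. On the 4.1a scale:

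blast % = b × (1 − E)

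At the minimum b = 20%:

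| E | Blast % of all nucleated cells |
|---|---|
| 50% | 0.20 × 0.50 = 10% |
| 70% | 0.20 × 0.30 = 6% |
| 75% | 0.20 × 0.25 = 5% |
| 80% | 0.20 × 0.20 = 4% |
| 90% | 0.20 × 0.10 = 2% |

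The value is below 5% when E > 1 − 0.05/b. That is E above 75% for b = 20%, 80% for b = 25%, 83.3% for b = 30% and 87.5% for b = 40%.

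**3. Pure erythroid leukemia.** More than 80% of cells are erythroid, so fewer than 20% are non-erythroid. With b at or below 25%, blasts are under 0.25 × 20% = 5%. With no myeloblasts they are 0%.

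**4. Which cohort.** Item 2 of 5.1b requires more than 5% blasts in Cohort 2, which is incompatible with fewer than 5%. Only Cohort 1 can contain a patient whose marrow is below the limit at entry.

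**5. Effect on the Cohort 1 test.** The number k of such patients is an assumption, because the documents give none. If all k are certain to be scored CRi and the other 37 − k respond at 20%, the false-positive probability is P(Bin(37 − k, 0.20) ≥ 12 − k):
- k = 0: 0.052
- k = 1: 0.089
- k = 2: 0.146

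**6. If scoring is not certain.** For one patient scored CRi with probability q (also assumed), the probability is q × P(Bin(36, 0.20) ≥ 11) + (1 − q) × P(Bin(36, 0.20) ≥ 12). The first term is 0.0889. The second follows from step 1: (0.0517 − 0.20 × 0.0889)/0.80 = 0.0424.
- q = 0.3: 0.3 × 0.0889 + 0.7 × 0.0424 = 0.056
- q = 0.5: 0.066
- q = 0.7: 0.075

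**The case against.** **The link from 4.1a to 10.1 is inferred.** Section 4.1 is headed as diagnostic criteria. Section 10.1 does not refer back to it and cites published working-group response recommendations instead. This is true, but the protocol offers no other blast percentage, so a site following the text would use 4.1a.

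**Section 10.2 has a category for persistent leukemia.** It does not help: 10.2 classifies only patients who have failed to reach CR, CRi or PR.

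**Nobody is scored before treatment.** This stands. Section 7.7 places the response marrow after Induction. A wrong CRi needs a patient who survives to assessment, has a marrow taken, has no Auer rods or extramedullary disease, and still has the disease. A marrow that truly clears is a real response. Hence 0.089 and 0.146 are upper bounds for the assumed counts, and a reader should not take them as the trial's error rate. A count of zero is also plausible.

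**Not all erythroid disease is affected.** This also stands. Erythroid/myeloid cases with 50% to 75% erythroid cells have at least 5% blasts at entry and cannot meet CRi unchanged. It would be too strong to say that both cohorts, or all erythroid leukemias, are exposed.

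**Relapse and RFS.** A reader might infer that relapse goes undetected in these patients and that RFS is therefore overstated. The documents do not support that. Section 10.3 also counts leukemic blasts in blood and extramedullary disease, and 10.4 counts death from any cause. Only the marrow part of the definition is insensitive.

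**The benchmark.** The protocol does not say which response definition lies behind the 20% null. If it was the same one, part of the bias is shared.

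**Conclusion.** The concern holds for Cohort 1 in a limited form. As written, sections 4.1, 5.1a and 10.1 together allow an eligible patient's marrow to meet a 4.1b diagnosis of AML and the CRi marrow criterion at once. The error comes from a stated rule, and no other section corrects it.

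Its size is unknown and probably small. The false-positive probability runs from 0.052 with no such patients to at most 0.089 with one or 0.146 with two. Those counts, and the certainty of CRi scoring, are assumptions. Overstatement of RFS is possible but not shown. The Cohort 2 test is not exposed to an unchanged entry marrow being scored CRi, and the 12-of-37 rule itself needs no change.

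**What to change.** Reconcile 10.1 and 10.3 with 4.1b in two sentences:
- in 10.1, a marrow that still meets a 4.1b diagnostic definition of AML cannot be scored CR or CRi, whatever its blast percentage under 4.1a;
- in 10.3, a marrow that again meets such a definition counts as relapse.

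A general switch to a non-erythroid denominator for response is not advisable. At 80% erythroid cells, blasts making up 1% of all cells become 1/20 = 5% of non-erythroid cells, and a recovering, erythroid-rich remission marrow would fail the 5% limit. Under the wording above, that marrow does not meet the erythroid/myeloid definition, which needs 20%.

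The cost is slight. The reading uses the marrow already required by 7.7, and sample size, decision rule and treatment are unchanged. Pure erythroid disease will still need a morphologic judgement on whether the erythroid population is neoplastic, as it does at diagnosis. Where responses have already been scored, the check is to re-read the post-induction marrow reports of Cohort 1 patients with erythroid leukemia who were counted as CR or CRi, and to report how many there were.
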